# 6.3 Efficacy

The following primary and secondary CV efficacy variables will be adjudicated by the independent, blinded CEC. For documents to be sent to the CEC, refer to *Investigator Manual for Events to be Adjudicated*.

## 6.3.1 Primary efficacy variable

The primary outcome efficacy variable of the study is the composite endpoint of CV death, non-fatal MI or non-fatal ischaemic stroke (time to first event).

This is also the primary safety outcome variable of the study.

#### 6.3.2 Secondary efficacy variable

The **first** secondary efficacy variable is the composite endpoint of CV death, non-fatal MI, non-fatal ischaemic stroke, hospitalisation for heart failure, hospitalisation for unstable angina pectoris or hospitalisation for coronary revascularisation.

#### The next secondary efficacy variable is time to any documented death

## 6.3.3 Other efficacy variables

The other efficacy variables comprise the following:

- Addition of new antidiabetic medication or  $\geq 1$  step increase in dose for an oral antidiabetic drug or  $\geq 25\%$  increase in insulin dose which lasts for  $\geq 3$  months
- Start of insulin regimen which lasts for  $\geq 3$  months

- Hospitalisation for hypoglycaemia
- Cardiovascular death
- Non-fatal MI
- Non-fatal ischaemic stroke
- Hospitalisation for heart failure
- Hospitalisation for unstable angina pectoris
- Hospitalisation for coronary revascularisation
- Primary endpoint composite (CV death, non-fatal MI or non-fatal ischaemic stroke) occurring during the first year of follow-up and after the first year
- Documented laser treatment due to development of and/or deterioration in diabetic retinopathy
- Diabetic renal disease progression (diabetic nephropathy) as assessed by the following:
  - Reduction from baseline of the microalbumin/creatinine ratio
  - Categorical change from baseline in albuminuria (normoalbuminuria, microalbuminuria and/or macroalbuminuria)
  - Doubling of serum creatinine levels
  - Initiation of chronic dialysis and/or renal transplant and/or a serum creatinine >6.0 mg/dL (> 530 µmol/L)
- The composite event of death, doubling of serum creatinine, initiation of chronic dialysis, renal transplant, or a serum creatinine > 6.0 mg/dL (> 530 µmol/L)

#### 6.3.4 Exploratory variables

Exploratory variables include the following:

- Future biological research, see Appendix H
- Future genetic research, see Appendix F
- Change from baseline in HbA1c, FPG and HOMA- $\beta$  and achievement of HbA1c  $\leq 6.5\%$  and <7%.

## 6.3.5 Laboratory variables

The laboratory variables that will be measured to assess efficacy and visits at which they will be measured are shown in Table 3. These variables will be assessed at a central laboratory (Quintiles Central Laboratory Services). For information on methods of collection, assessment, labelling, storage and shipment of samples, see the Laboratory Manual. Urinary albumin excretion will be measured as the albumin/creatinine ratio (mg/g) for assessment of diabetic nephropathy.

Regarding procedures for blood collection, labelling and shipment, see Section 7.

Patients should be instructed to abstain from all food for 8 hours prior to Visits 1, 5 and the End of Treatment/Closing Visit, when fasting samples are to be collected; however, drinking water is allowed.

# 6.4 Safety

The methods for collecting safety data by AstraZeneca and BMS, per the Safety Data Exchange Agreement between these 2 companies, are described below.

The PI is responsible for ensuring that all staff involved in the study are familiar with the content of this section.

## 6.4.1 Definition of adverse events

An adverse event (AE) is the development of an undesirable medical condition or the deterioration of a pre-existing medical condition following or during exposure to a pharmaceutical product, whether or not considered causally related to the product. An undesirable medical condition can be symptoms (eg, nausea, chest pain), signs (eg, tachycardia, enlarged liver) or the abnormal results of an investigation (eg, laboratory findings, ECG). In clinical studies, an AE can include an undesirable medical condition occurring at any time, even if no study treatment has been administered.

The term AE is used to include both serious and non-serious AEs.

# 6.4.1.1 AEs of special interest

Secondary objectives will include an assessment of the long-term effects of saxagliptin on the following AEs of special interest: decrease in lymphocyte counts, decrease in thrombocyte counts, the risk of severe infections, hypersensitivity reactions, liver abnormalities, bone fractures, pancreatitis, skin reactions and renal abnormalities. For hypersensitivity reactions, especially angioedema, reports will include detailed information on concomitant use of an angiotensin-converting enzyme inhibitor or an angiotensin-receptor blocker. For cases of pancreatitis, serum lipase and/or amylase concentrations with accompanying normal ranges and any imaging study reports will be included in the narratives.

Specific clinical details for decrease in lymphocyte counts or thrombocyte counts, severe infections, hypersensitivity reactions, liver abnormalities, skin reactions and renal

abnormalities, bone fractures, pancreatitis, opportunistic infections and liver abnormalities with serum AST or ALT greater than or equal to 3 times ULN and serum TB greater than 2 times ULN or evidence of jaundice will be captured in supplemental CRF pages regardless of seriousness.

See Appendix I for information on identification of AEs of special interest.

## 6.4.1.2 Hypoglycaemic events

In this study a hypoglycaemic event will be defined as either minor or major. Regardless of symptoms any recorded blood glucose <54 mg/dL (<3.0 mmol/L) will be considered an hypoglycaemic event and will trigger an hypoglycaemia adverse event report. The patient will be provided a patient diary to record symptoms of hypoglycaemic episodes **and** any blood glucose values measured in connection with the episode as well as any value <54 mg/dL (<3.0 mmol/L).

A hypoglycaemic event can be either:

- An episode with symptoms and confirmed low glucose
- An episode with low glucose
- An episode with symptoms when glucose was not measured

**Minor hypoglycaemic events** are considered when there is an awareness of the event, the event is tolerated and the patient recovers by her/himself. In addition the events resolves within 30 minutes of ingestion of carbohydrates (if possible confirmed with a fingerstick value). A measurement of blood glucose <54 mg/dL (<3.0 mmol/L) without symptoms, is also considered an AE.

A major hypoglycaemic event is an event requiring assistance of another person to actively administer carbohydrate, glucagons, or other resuscitative actions. These episodes may be associated with sufficient neuroglycopenia to induce seizure or coma. Plasma glucose measurements may not be available during such an event, but neurological recovery attributable to the restoration of plasma glucose to normal is considered sufficient evidence that the event was induced by a low blood glucose concentration.

Data to be collected for each hypoglycaemic event will include but are not limited to:

- Date of start and stop, and time of the day for start
- Maximal intensity (mild or severe)
- If fingerstick value obtained and the blood glucose value
- Action taken in regard to the investigational therapy or other anti-diabetic agents

The patient diary will be reviewed and data regarding hypoglycaemic events transcribed into the hypoglycaemia CRF at each clinical visit. A hypoglycaemic event that meets any criterion for seriousness should be reported as an SAE. A new diary for the next period will be provided the patient if needed. If a major hypoglycaemic event, or more than one minor event occur since the last visit, the patient should contact the investigator.

Hospitalisation for hypoglycaemia will be recorded with admission and discharge dates.

#### 6.4.2 Definition of serious adverse event

An SAE is an AE occurring during any study period (ie, treatment, follow-up) and at any dose of the IPs (including placebo) that fulfils 1 or more of the following criteria:

- Results in death
- Is immediately life-threatening
- Requires in-patient hospitalisation or prolongation of existing hospitalisation
- Results in persistent or significant disability or incapacity
- Is a congenital abnormality or birth defect
- Is an important medical event that may jeopardise the patient or may require medical intervention to prevent one of the outcomes listed above

In addition, the following events (regardless of whether or not they meet any of the serious criteria above) will be collected as SAEs:

- Cancer
- Drug dependency/abuse

For the purposes of regulatory reporting, the following events/medical concepts should be transmitted as described in Section 6.4.4 in the same timelines as SAEs.

- Pancreatitis
- Opportunistic infections (eg, tuberculosis, Herpes zoster, cytomegalovirus, *Pneumocystis jirovecii*, etc)
- Serum AST or ALT greater than or equal to 3 times ULN, and serum TB greater than 2 times ULN or evidence of jaundice.
- Angioedema
- Anaphylaxis

#### • Steven Johnson syndrome

For further guidance on the definition of an SAE, see Appendix B.

#### 6.4.3 Recording of adverse events

#### Time period for collection of AEs

AEs will be collected from time of first administration of IPs throughout the study until and including the last visit/contact (ie, Closing Visit).

SAEs will be collected from the signing of informed consent throughout the study until and including the last visit/contact (ie, Closing Visit).

#### Follow-up of unresolved AEs

Any AEs that are unresolved at the last visit/contact (ie, Closing Visit) in the study are followed up by the Investigator for as long as medically indicated, but without further recording in the CRF. AstraZeneca Patient Safety, BMS GPV&E and TIMI retain the right to request additional information for any patient with ongoing AE(s)/SAE(s) at the end of the study, if judged necessary. The requirement to follow-up is not intended to delay database lock or production of the clinical report. Both these activities should proceed as planned with ongoing AEs if necessary.

Any follow-up of ongoing SAEs after database lock will be reported to the TIMI study group representative, who will notify the appropriate BMS GPV&E contact.

#### AEs reported after the end of study

Only unsolicited SAEs will be collected for a period of up to 30 days after the end of the study. All SAEs will be recorded and reported to BMS GPV&E (see Section 6.4.4).

#### Variables

The following variables will be collected for each AE:

- AE (verbatim)
- Date when the AE started and stopped
- Maximum intensity
- Whether or not the AE is serious
- Investigator causality rating against the investigational product (yes or no)
- Action taken with regard to IP
- Whether or not AE caused patient's withdrawal from IP

• Outcome

In addition, the following variables will be collected for SAEs:

- Date AE met criteria for serious AE
- Date Investigator became aware of serious AE
- Reason for classification as serious
- Date of hospitalisation
- Date of discharge
- Reason for hospitalisation
- Probable cause of death
- Date of death
- Autopsy performed
- Causality assessment in relation to study procedure(s)
- Causality assessment in relation to other medication
- Causality assessment in relation to additional study drug
- Description of AE.

It is important to distinguish between serious and severe AEs. Severity is a measure of intensity whereas seriousness is defined by the criteria in Section 6.4.2. An AE of severe intensity need not necessarily be considered serious. For example, nausea that persists for several hours may be considered severe nausea, but not an SAE. On the other hand, a stroke that results in only a limited degree of disability may be considered a mild stroke but would be an SAE. If the intensity of an AE changes, only the maximum intensity of the event will be recorded.

Intensity is defined as 1 of the following:

- Mild (awareness of event but easily tolerated)
- Moderate (discomfort enough to cause some interference with usual activity)
- Severe (inability to carry out usual activity)

Very severe (debilitating, significantly incapacitates patient despite symptomatic therapy).

#### **Causality collection**

The Investigator will assess causal relationship between IP and each AE, and answer "yes" or "no" to the question "Do you consider that there is a reasonable possibility that the event may have been caused by the investigational product?" If there is any valid reason, even if undetermined or untested, for suspecting a possible cause-and-effect relationship between the IP and the occurrence of the AE, then this should be answered "yes." Otherwise, if no valid reason exists for suggesting a possible relationship, then this should be answered "no." If more than 1 AE is identified, a causality assessment must be made for each AE.

For SAEs, causal relationship will also be assessed for other medication and study procedures. Note that for SAEs that could be associated with any study procedure the causal relationship is implied as "yes."

A guide to the interpretation of the causality question is found in Appendix B.

#### AEs based on signs and symptoms

All AEs spontaneously reported by the patient or reported in response to the open question from the study personnel: "Have you had any health problems since the previous visit?" or revealed by observation will be collected and recorded in the CRF. When collecting AEs, recording diagnoses is preferred (when possible) to recording a list of signs and symptoms. However, if a diagnosis is known and there are other signs or symptoms that are not generally part of the diagnosis, the diagnosis and each sign or symptom will be recorded separately.

#### AEs based on examinations and tests

The results from protocol-mandated laboratory tests and vital signs will be summarised in the Clinical Study Report (CSR). Deterioration as compared to baseline in protocol-mandated laboratory values, vital signs and other safety variables should therefore only be reported as AEs if they fulfil any of the SAE criteria or are the reason for discontinuation of treatment with the IP.

If deterioration in a laboratory value/vital sign is associated with clinical signs and symptoms, the sign or symptom will be reported as an AE and the associated laboratory result/vital sign will be considered as additional information. Wherever possible; the reporting Investigator uses the clinical, rather than the laboratory term (eg, anaemia vs low haemoglobin value). In the absence of clinical signs or symptoms, clinically relevant deteriorations in non- mandated parameters should be reported as AE(s).

Any new or aggravated clinically relevant abnormal medical finding at a physical examination as compared with the baseline assessment will be reported as an AE.

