# 2.3 Safety objectives

#### 2.3.1 Secondary safety objectives

Safety and tolerability will be evaluated by assessment of overall AEs and AEs of special interest. These will include assessment of the long-term effects of saxagliptin on decrease in lymphocyte counts, decrease in thrombocyte counts, severe infections, hypersensitivity reactions, liver abnormalities, bone fractures, pancreatitis, skin reactions and renal abnormalities. See Appendix I for information on identification of these events.

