#### Visits 3 and 7 (12 and 36 months)

Suspected clinical events and AEs will be recorded. If required, a targeted physical examination will be done. Vital signs (pulse and BP) as well as blood sampling (fasting not required) for laboratory assessments of HbA1c, CBC with differential, serum creatinine, TB, ALT and AST will be done. Women of childbearing potential will be tested for pregnancy. IP will be returned and compliance assessed and new bottles of IP via the IVRS/IWRS will be dispensed. The EQ-5D will be completed. Concomitant medication and weight will be recorded. Added assessments of urinalysis (microalbumin and creatinine) will be done. Diet and life-style advice will be given.

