#### 12.1.3.5 Safety endpoints

Safety is evaluated by the following endpoints:

• Secondary safety endpoints:

- Incidence of overall AEs and AEs of special interest
- Other safety endpoints:
  - Changes from baseline in laboratory tests, pulse, BP, waist circumference and body weight
  - Incidence of hypoglycaemic events, cancers and peripheral oedemas

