### 12.2.2 Safety analyses

The primary safety endpoint is the time to first event included in the composite endpoint of CV death, non-fatal MI or non-fatal ischaemic stroke. The primary safety analysis will be based on the ITT population, using events adjudicated and confirmed by the independent CEC.

The baseline value of each laboratory parameter or physical examination endpoint is defined as the last assessment before the date and when available, time of the first dose of double-blind study drug.

The number and percent of patients with an AE will be summarised for each treatment group. Changes from baseline to each scheduled time point for each clinical laboratory test, BP and pulse will be summarised by treatment group. In addition, the number and percent of patients with a predefined marked abnormality in clinical laboratory tests will be summarised by treatment group.

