# **2** DECREASE IN LYMPHOCYTE OR THROMBOCYTE COUNTS

Adverse events related to decrease in lymphocyte and thrombocyte counts will be identified using the following MedDRA preferred terms (PTs).

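### Lymphocyte and thrombocyte decreases are counted from adverse event terms only, while the site reporting rule keeps most types of laboratory-detected fall out of the adverse event data

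*Protocol*

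**What the plan says.** Protocol section 2.3.1 sets as a secondary safety objective the "assessment of the long-term effects of saxagliptin on decrease in lymphocyte counts, decrease in thrombocyte counts" and other named events, and refers to Appendix I for how they are identified. Section 12.1.3.5 gives the matching secondary safety endpoint as "Incidence of overall AEs and AEs of special interest". Changes in laboratory tests are listed below it, under other safety endpoints.

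Appendix I section 2 reads "Adverse events related to decrease in lymphocyte and thrombocyte counts will be identified using the following MedDRA preferred terms (PTs", followed by seven terms for lymphopenia and ten for thrombocytopenia. It gives no count threshold.

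The blood count is a scheduled test. For Visits 3 and 7, for example, "laboratory assessments of HbA1c, CBC with differential, serum creatinine, TB, ALT and AST will be done". Table 3 also places it at Visits 1, 5 and 9 and at end of treatment, with analysis at a central laboratory.

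Section 6.4.3, on AEs based on examinations and tests, first explains that "The results from protocol-mandated laboratory tests and vital signs will be summarised in the Clinical Study Report (CSR"). It then says that deterioration in such values "should therefore only be reported as AEs if they fulfil any of the SAE criteria or are the reason for discontinuation of treatment" with investigational product. Section 6.4.1.1 says that clinical details of a list of events, in which lymphocyte and thrombocyte decreases come first, "will be captured in supplemental CRF pages regardless of seriousness".

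**The concern.** A fall in a blood count is a laboratory finding before it is anything else. If sites follow section 6.4.3, a fall that is neither serious nor the reason for stopping treatment is not entered as an AE, so it acquires none of the preferred terms that Appendix I searches for. It then drops out of the endpoint meant to answer the objective.

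Sites also receive two instructions that do not fit together: withhold the AE report for a non-serious fall, but record its details on a supplemental page. Nothing says which prevails. At stake are the completeness of a secondary safety tabulation and the clinical detail behind non-serious cases, which cannot reliably be rebuilt once the trial is over.

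**Working it through.** The check is mainly a comparison of texts; the Protocol states no figure on this point to reproduce.

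**Step 1: what the endpoint counts.** Sections 2.3.1 and 12.1.3.5 together make it an incidence of AEs of special interest. For these two items Appendix I section 2 supplies preferred terms and nothing else.

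**Step 2: which falls can acquire such a term.** The blood count is mandated, so section 6.4.3 applies:

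| Laboratory-detected fall | Reported as an AE under section 6.4.3? | Reaches the Appendix I search? |
|---|---|---|
| Meets a seriousness criterion | Yes | Yes, if coded to a listed term |
| Reason for stopping treatment | Yes | Yes, if coded to a listed term |
| Neither, but with signs or symptoms | The sign or symptom is the AE; the count is additional information | Not assured |
| Neither, and no signs or symptoms | No | No |

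The study-specific discontinuation criteria in section 5.8 cover liver tests and pregnancy and contain none for blood counts. The second row therefore depends on judgement or the patient's choice.

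**Step 3: compare with other events in Appendix I.** Section 6 (liver) has laboratory criteria beside its term list. Section 10 (renal) includes doubling of creatinine beside its terms. Section 2, whose subject is itself a laboratory count, has no such criterion.

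**Step 4: what the by-arm laboratory analysis provides.** Section 12.2.2 plans changes from baseline for each clinical laboratory test and says that "the number and percent of patients with a predefined marked abnormality in clinical laboratory tests will be summarised by treatment group". This captures the falls irrespective of AE reporting, but the section does not connect them to the events of special interest, and section 12.1.3.5 places laboratory change in the lower tier.

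**Step 5: size.** Let p be the proportion of an arm with a laboratory-detected fall past a given limit, and s the share of those falls that also appear under a listed term. The special-interest tabulation shows s × p of them and misses (1 − s) × p. If s is the same in both arms, a difference p1 − p0 appears as s × (p1 − p0); the ratio is preserved in expectation but rests on fewer events. The documents give neither p nor s. On the documents alone s can lie anywhere from 0 to 1, so the uncaptured share can be anything from 0% to 100%. Only the direction is fixed: the tabulation cannot over-count these falls.

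**The case against.** The strongest reply is that the trial does not lose the cases. Blood counts are measured centrally on the same schedule in both arms and summarised by arm, and section 6.4.3 gives that as its reason for not duplicating them as AEs. The objective concerns counts, and count data address it directly. This stands. What remains is that the endpoint named for the objective is the AE-based one, and the laboratory summary is neither linked to it nor a trigger for the supplemental page.

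A second reply is that section 6.4.1.1 does not make an AE report the condition for a supplemental page and can be read as the specific rule overriding the general one. Section 9.3 also asks monitors to see that data on events of special interest are captured, and section 11.2.2 cites marked haematological abnormalities as examples of significant AEs that are neither serious nor a cause of discontinuation. This rules out saying that the page would never be completed. It also shows that the sections need reconciling.

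A third reply is that Appendix I is open to updates and a laboratory flag could be specified in an analysis plan. That would recover the counts. It would not recover clinical detail that sites were not told to record, and both the identification rule and the recording rule are fixed in this Protocol.

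A reader might go further and infer that most cases will be missed, or that both arms will show near-zero counts that look reassuring. The documents support neither: they give no frequency of such falls and no capture share, and several thrombocytopenia terms, such as idiopathic thrombocytopenic purpura, are clinical diagnoses that would be reported anyway. Nor does a loss-of-power calculation help. Its inputs would have no source in the Protocol, and the synopsis says safety variables are summarised descriptively.

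**Conclusion.** The point holds as an inconsistency with a known direction and an unknown size. Followed as written, the rules give a special-interest incidence for lymphocyte and thrombocyte decreases that is biased low for laboratory-detected falls, and they give sites conflicting instructions on non-serious cases. This assumes that sites apply section 6.4.3 literally and that Appendix I section 2 is the complete identification rule.

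The harm is limited. The measured counts remain in the database with a planned by-arm summary, so the objective can still be examined, though not through the endpoint assigned to it. What may be lost outright is clinical detail on non-serious falls. The primary endpoint, type I error and sample size are untouched. It is worth correcting because the remedy is specific and cheap, but it does not threaten the trial's main conclusions.

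**What to change.** 1. In Appendix I section 2, add a central-laboratory criterion beside the preferred terms, in the manner of sections 6 and 10: any post-baseline lymphocyte or platelet value meeting the predefined marked-abnormality limit already foreseen in section 12.2.2. Report the special-interest incidence on that basis as well as by preferred term.
2. In section 6.4.3, state that laboratory-defined events of special interest are exempt from the restriction to serious or treatment-stopping deteriorations.
3. In section 6.4.1.1, state that meeting the laboratory criterion triggers the supplemental CRF page, so that the two sections agree.

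The cost is Protocol and appendix wording, one derivation from central-laboratory data already collected, and some additional CRF pages. No new samples are needed, and sample size, power and alpha do not change.
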